**Description:**

- The purpose of this RAP is to describe the planned analyses and output to be included in the Clinical Study Report for Protocol 207652.
- This RAP will be provided to the study team members to convey the content of the final Statistical Analysis Complete (SAC) deliverable.

## 1. INTRODUCTION

The purpose of this reporting and analysis plan (RAP) is to describe the analyses to be included in the Clinical Study Report for 207652 Protocol:

Revision Chronology:		
2017N312753_00	01-JUN-2017	Original
2017N312753_01	20-JUL-2018	Amendment 1

All decisions regarding final analysis, as defined in this RAP document, have been made prior to Database Freeze (DBF) of the study data.

## 2. SUMMARY OF KEY PROTOCOL INFORMATION

### 2.1. Changes to the Protocol Defined Statistical Analysis Plan

There were no changes or deviations to the Amendment 1 planned statistical analysis specified in the protocol [Dated: 20/JUL/2017].

### 2.2. Study Objective(s) and Endpoint(s)

Objectives	Endpoints
Primary Objectives	Primary Endpoints

 
To evaluate the bioequivalence of Paroxetine IR tablets manufactured in GSKT and Mississauga sites in healthy Chinese participants under fasting and fed conditions.
 
	
 
<math>AUC_{(0-\infty)}</math>, <math>AUC_{(0-t)}</math> and <math>C_{max}</math> of Paroxetine IR tablets
 

Secondary Objectives	Secondary Endpoints

 
To assess the safety and tolerability of dosing with Paroxetine IR tablets in healthy Chinese participants.
 
	
 
Safety and tolerability as measured by adverse events, vital signs, ECG and clinical laboratory measurements.
 

 
To obtain the pharmacokinetic profile of Paroxetine IR tablets in healthy Chinese participants.
 
	
 
<math>T_{max}</math>, <math>\lambda_z</math>, and <math>t_{1/2}</math> of Paroxetine IR as data permit.
 

### 2.3. Study Design

Overview of Study Design and Key Features	

The diagram illustrates the study design timeline from Day -7 to Day 28. It is divided into several phases: Screening (Days -7 to -1), Randomization (Day 0), First Period (Days 1-5), Washout (Days 6-11), Second Period (Days 12-16), and Follow-up (Days 17-28). Two groups are shown: Fed Group and Fasting Group. Each group is randomized into two sequences: AB and BA. In the AB sequence, Drug A is administered on Day 1 and Drug B on Day 12. In the BA sequence, Drug B is administered on Day 1 and Drug A on Day 12. Sampling points are indicated by orange boxes between Day 1-5 and Day 12-16. A vertical dashed line at Day 0 marks the start of randomization.
	
Design Features	
 
A single dose, open-label, randomized, two-way crossover study to demonstrate the bioequivalence of Paroxetine IR tablets manufactured in GSKT (A) and Mississauga (B) sites in healthy Chinese participants under fasting and fed conditions.
 

Dosing	
 
On Day 1, each enrolled participant will take a single dose of Paroxetine IR 40mg (20mg*2 tablets) A or B.
 
Following a washout from Day 6 to Day 11, participants will be crossed over in Period 2 to receive the treatment that they did not receive in Period 1. Eligible participants will take Paroxetine IR 40mg (20mg*2 tablets) A or B once on Day 12.
 

Treatment Assignment	
 
The whole study will be divided into two groups, one for fasting condition and another for fed condition. For each group, eligible participants will be randomized to either AB or BA treatment sequence according to 1:1 ratio.
 
Participants will be randomly assigned to either regimen sequence (AB or BA) in a balanced manner to ensure similar proportions of participants on each sequence, according to a randomization schedule prepared in advance of the study by Statistics, GlaxoSmithKline, using internal validated software (i.e. RandAll).
 

Interim Analysis	
 
No interim analysis is planned.
 

### 2.4. Statistical Hypotheses

This study is designed to test the bioequivalence of Paroxetine IR 20mg×2 GSKT tablets and Paroxetine IR 20mg×2 Mississauga tablets in healthy Chinese participants under fasting and fed conditions. The null hypothesis is that the true ratio of the geometric mean of the test treatment (Paroxetine IR 20mg×2 GSKT tablets) to the geometric mean of the reference treatment (Paroxetine IR 20mg×2 Mississauga tablets),  $\mu(\text{test})/\mu(\text{reference})$ , for  $AUC_{(0-\infty)}$ ,  $AUC_{(0-t)}$  ( $AUC_{(0-t)}$  only if  $AUC_{(0-\infty)}$  can't be accurately determined) and  $C_{\text{max}}$

of Paroxetine, is either less than 0.80 or greater than 1.25. The alternate hypothesis is that the true ratio of the test treatment geometric mean to the reference treatment geometric mean is greater than / equal to 0.80 and less than / equal to 1.25. Symbolically, this is expressed as follows:

$$H(0): \mu(\text{test})/\mu(\text{reference}) < 0.80 \text{ or } \mu(\text{test})/\mu(\text{reference}) > 1.25,$$

i.e., treatments are not bioequivalent.

Versus

$$H(1): 0.80 \leq \mu(\text{test})/\mu(\text{reference}) \leq 1.25,$$

i.e., treatments are bioequivalent.

For each PK parameter designated as a primary endpoint, a two one-sided t-test (TOST) procedure [Schuirmann, 1987] with  $\alpha=0.05$  for each one-sided test will be used to test this set of hypotheses. This is equivalent to requiring that a 90% interval for the true ratio of test to reference geometric means fall entirely within the range of 0.80 to 1.25.

### **3. PLANNED ANALYSES**

#### **3.1. Interim Analyses**

No interim analysis is planned.

#### **3.2. Final Analyses**

The final planned primary analyses will be performed after the completion of the following sequential steps:

1. All participants have completed the study as defined in the protocol.
2. All required database cleaning activities have been completed and final database release (DBR) and database freeze (DBF) (both the CRF data and PK data) has been declared by Data Management.

All the analyses will be displayed separately for each group (Fasting or Fed).

## 4. ANALYSIS POPULATIONS

Population	Definition / Criteria	Analyses Evaluated
All participants	
 
All participants who signed the ICF.
 
	
 
Subject population
 
Screen failures
 

Safety Population	
 
All randomized participants who take at least one dose of study treatment.
 
Participants will be analysed according to the treatment they actually received.
 
	
 
Study Population
 
Safety
 

Pharmacokinetic (PK) Population	
 
All randomized participants who take at least one dose of study treatment and provide at least one evaluable pharmacokinetic concentration data.
 
Participants will be analysed according to the treatment they actually received.
 
	
 
PK
 

Bioequivalence (BE) Analysis Population	
 
All randomized participants who complete all the planned treatments and provide at least one evaluable primary PK parameter data from both period 1 and period 2.
 
Participants will be analysed according to the treatment they actually received.
 
	
 
Bioequivalence analysis
 

Refer to [Appendix 7](#): List of Data Displays which details the population used for each display.

### 4.1. Protocol Deviations

Important protocol deviations (including deviations related to study inclusion/exclusion criteria, conduct of the trial, patient management or patient assessment) will be summarised and listed.

Protocol deviations will be tracked by the study team throughout the conduct of the study in accordance with the Protocol Deviation Management Plan.

- Data will be reviewed prior to freezing the database to ensure all important deviations and deviations which may lead to exclusion from the analysis are captured and categorised on the protocol deviations dataset.
- This dataset will be the basis for the summaries and listings of protocol deviations.

A separate summary and listing of all inclusion/exclusion criteria deviations will also be provided. This summary will be based on data as recorded on the inclusion/exclusion page of the eCRF.

## 5. CONSIDERATIONS FOR DATA ANALYSES AND DATA HANDLING CONVENTIONS

### 5.1. Study Treatment

Treatment Group Descriptions			
Randomization System		Data Displays for Reporting	
Code	Description	Description	Order in TLF
A	Paroxetine IR GSKT tablets 20mg*2 tablets	40mg GSKT	1
B	Paroxetine IR Mississauga tablets 20mg*2 tablets	40mg Mississauga	2

Treatment comparisons will be displayed as A vs B.

### 5.2. Baseline Definitions

For all endpoints (except as noted in baseline definitions), the baseline value will be the latest pre-dose assessment with a non-missing value, including those from unscheduled visits. If time is not collected, Day 1 assessments are assumed to be taken prior to first dose and used as baseline.

Parameter	Study Assessments Considered as Baseline			Baseline Used in Data Display
	Screening	Day 0	Day 1 (Pre-Dose)	
Safety				
Laboratory	X			Screening
Vital Signs	X	X	X	Latest available pre-dose assessment
Weight, Height	X	X		Latest available pre-dose assessment
12-Lead ECG	X			Screening

Unless otherwise stated, if baseline data is missing no derivation will be performed and baseline will be set to missing. The mean of replicate assessments at any given time point will be used as the value for that time point.

Definition	Reporting Details
Change from Baseline	= Post-baseline Value – Baseline
% Change from Baseline	= 100 x [(Post-baseline Value – Baseline) / Baseline]

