#### **7.4.1. Vital Signs**

Each vital sign parameter at every assessed time point will be summarized. The change from baseline for each vital sign parameter will also be summarized.

A listing of all vital sign values for subjects who had any value of potential clinical importance during the study will be provided. A listing of vital sign values of potential clinical importance only will also be provided.

The summary will be displayed overall for Screening, Day 0 and Day 11, and by treatment group A/B (A: Paroxetine IR 40 mg GSKT tablet; B: Paroxetine IR 40 mg Mississauga tablet) for other time points.

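### Vital signs have only a pre-Day 1 baseline, so changes shown by product after the Day 12 dose start from a reading at least 11 days before that dose, taken before the other product was given

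*SAP*

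**What the plan says.** Section 2.3 sets out a two-period crossover with one dose on Day 1 and one on Day 12: "Following a washout from Day 6 to Day 11, participants will be crossed over in Period 2". Sequences AB and BA are allocated 1:1 within each of the fasting and fed groups.

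Section 5.2 gives a general rule: "the baseline value will be the latest pre-dose assessment with a non-missing value, including those from unscheduled visits". The rule does not say which of the two doses is meant. The table beneath it does: its only columns are Screening, Day 0 and Day 1 (Pre-Dose). Vital signs are marked in all three, and the value used for display is the "Latest available pre-dose assessment". A fallback for readings without a recorded time also points to the first dose: "Day 1 assessments are assumed to be taken prior to first dose and used as baseline". Change is "Post-baseline Value – Baseline", with nothing to distinguish the periods.

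Section 7 assigns safety readings to A or B by assessment date. Section 7.4.1 plans the change summary ("The change from baseline for each vital sign parameter will also be summarized") and fixes the layout: "The summary will be displayed overall for Screening, Day 0 and Day 11, and by treatment group A/B" for the remaining time points. Section 10.7.5 lists the change tables as 2.41 (fed) and 2.42 (fasting).

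**The concern.** A change displayed under a product should describe what happened after that product was given. In Period 1 it does, because the baseline can be a reading from the day of dosing or shortly before. In Period 2 the same baseline is carried forward past the first product, its sampling days and the washout. The resulting change mixes any response to the second product with whatever moved the participant's level in between, such as settling into the unit or a residual effect of the first product.

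Section 7.4.1 itself treats Day 11 like Day 0, as a point belonging to neither product. Day 0 may serve as a baseline for Period 1, but Day 11 may not serve for Period 2. Vital signs are one of the named measures of the secondary safety endpoint in Section 2.2, so each product's change summary should be readable on its own.

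**Working it through.** The SAP states no figure on this point to reproduce. The check is day arithmetic on the stated schedule, followed by the expected effect of a shift.

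**Inputs.** From Section 2.3: doses on Days 1 and 12, screening from Day -7, sampling to Day 16, 1:1 sequences. From Section 5.2: permitted baseline days. From Section 7.4.1: vital signs available on Day 11.

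**Step 1: age of the baseline at the Period 2 dose** (12 minus baseline day).

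| Baseline reading | Days before the Day 12 dose |
|---|---|
| Day 1 pre-dose | 12 - 1 = 11 |
| Day 0, if Day 1 is missing | 12 - 0 = 12 |
| Screening at Day -7, if both are missing | 12 + 7 = 19 |
| Day 11, not permitted at present | 12 - 11 = 1 |

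Eleven days is thus the minimum. A reading on Day 16 would be 15 days from a Day 1 baseline but 4 days from the dose it is attributed to.

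**Step 2: effect of a shift.** Let d be the mean difference between the pre-Period 2 and pre-Period 1 levels, taken as the same in both sequences, and let s be the share of contributing participants in sequence AB. Those in AB receive B in Period 2; those in BA receive A.

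- *Tables by study day.* Rows up to Day 5 hold Period 1 data and are displaced by 0. Rows from Day 12 hold Period 2 data and are displaced by d for both A and B, so A minus B is displaced by d - d = 0.
- *Periods pooled by time from dosing.* A is displaced by (1 - s)d, B by sd, and A minus B by (1 - 2s)d.

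The SAP gives no value for d, so the following values are assumptions, in mmHg:

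| d | Period 2 rows, by study day | Each product, pooled, s = 0.50 | A minus B, pooled, s = 0.50 | A minus B, pooled, s = 0.55 |
|---|---|---|---|---|
| 1 | 1 | 0.5 | 0 | -0.1 |
| 2 | 2 | 1.0 | 0 | -0.2 |
| 5 | 5 | 2.5 | 0 | -0.5 |

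The 55% share is also an assumption. Some imbalance is possible, because the Safety Population in Section 4 requires only one dose and Section 10.4.1 does not replace withdrawals.

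**Step 3: which layout applies.** Section 7.4.1 names its time points by study day, which suggests the first. Section 10.2.2 bases summaries on nominal time from dosing, which makes the second plausible. The shells that would decide it are in separate documents (Section 10.8).

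**Step 4: with a Day 11 baseline.** The gap to the Period 2 dose falls from 11 days to 1, and d drops out of the Period 2 changes apart from any movement over that one day.

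**The case against.** The strongest defence is that a single untreated baseline is a recognised convention. It gives one reference free of either product, and Section 5.2 treats laboratory and ECG data in a similar way, with Screening as baseline. Under it, Tables 2.41 and 2.42 correctly show change from the pre-study state. That stands as a description, but the SAP does not state or justify this as a choice for a by-product crossover display, where the reader will take each column as change after that product.

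A second defence is that the general rule could be read as the latest reading before each period's dose. The closed list of visits does not allow that. If it was intended, the table needs correcting anyway. The sentence about Day 1 readings should not carry the argument alone, because it applies only where time is not collected; the table columns carry it.

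A reader might infer more than the SAP supports:

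- *That half the values in every product column are affected.* This depends on pooling periods, which the SAP does not settle.
- *That Day 11 is ignored.* It is displayed: "The summary will be displayed overall for Screening, Day 0 and Day 11". Its change from the pre-study baseline may be shown too, which would make the shift visible. It is only excluded as a baseline.
- *That the comparison of A with B is distorted.* With balanced sequences, complete data and a common d, the shift cancels.
- *That safety flags or the main result are affected.* The vital-sign limits in Section 10.5.3 are absolute, the SAP plans no formal test of vital signs, and the bioequivalence analysis does not use this baseline.

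**Conclusion.** The point holds as a limited one that is worth fixing. As written, every vital-sign change after the Day 12 dose is measured from a reading at least 11 days before that dose, and before the other product, while a reading one day before the dose is available. Any shift d enters in full in Period 2 rows, or at about half its size in each product column, depending on a layout the SAP leaves open.

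The day counts follow from the SAP. The size of d does not: it is unknown and may be small. The harm is confined to each product's own mean change and to individual Period 2 changes. The statement that A minus B is unaffected rests on three conditions: balanced sequences (needed in the pooled layout), complete data, and the same shift in both sequences.

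**What to change.** In Section 5.2, define a period-specific vital-sign baseline as the latest non-missing assessment before that period's dose, and apply it to Tables 2.41 and 2.42:

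- Period 1: Screening, Day 0 or Day 1 pre-dose, as now.
- Period 2: Day 11, or Day 12 pre-dose if such a reading is taken (the SAP does not show whether one is). Readings from Period 1 should not qualify.

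State in Section 7.4.1 whether the change tables run by study day or pool the periods by time from dosing.

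The change has a small downside. The Period 2 baseline may carry a residual effect of the first product, and it may come from the day before dosing where Period 1 has a same-day value. The Day 11 change from the pre-study baseline should therefore still be shown overall, so that any shift stays visible.

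The cost is a few lines of SAP text and one derived variable. Day 11 vital signs are already planned, so no new assessment is needed.

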### 5.3. Other Considerations for Data Analyses and Data Handling Conventions

Other considerations for data analyses and data handling conventions are outlined in the appendices:

Section	Component
10.1	Appendix 1: Study Phases and Adverse Events
10.2	Appendix 2: Data Display Standards & Handling Conventions
10.3	Appendix 3: Derived and Transformed Data
10.4	Appendix 4: Reporting Standards for Missing Data
10.5	Appendix 5: Values of Potential Clinical Importance

## **6. STUDY POPULATION ANALYSES**

### **6.1. Overview of Planned Study Population Analyses**

The study population analyses will be based on the “Safety” population, and displayed separately for each group (Fasting or Fed), unless otherwise specified. Screen failures will be listed based on the “All participants” population.

Study population analyses including analyses of subject’s disposition, protocol deviations, demographic and baseline characteristics and prior and concomitant medications will be based on GSK Core Data Standards. Details of planned study population data displays will be presented in [Appendix 7: List of Data Displays of Full RAP](#).

### **6.2. Subject’s Disposition**

The number and percentage of subjects who completed the study as well as subjects who withdrew prematurely from the study will be summarized by completion status and reason for withdrawal. A listing of the subjects who withdrew from the study prematurely will be provided.

The number of subjects included in the safety population, and those included in the PK population will be summarized. Subjects who are excluded from the safety population and those who are excluded from PK population will be listed with the corresponding reason.

Subject’s disposition summary will be displayed by “Total”.

### **6.3. Protocol Deviations**

A listing of the inclusion/exclusion criteria deviation record for all subjects with deviations will be provided. Other deviations will be noted as applicable, including use of prohibited concomitant medications during the study, incorrect study drug administration, and any other deviations deemed to have the potential for notably influencing the study results. A summary of important protocol deviations and by-subject listing of important protocol deviations will be provided.

The summary will be displayed by “Total”.

## **6.4. Demographic and Baseline Characteristics**

### **6.4.1. Demographic characteristics**

Demographic characteristics listed below will be summarized either with descriptive statistics for continuous variables or with frequencies and percentages for categorical variables. A by-subject listing of these characteristics will be provided.

- Continuous variables: Age, Height, Weight, and Body mass index (BMI)
- Categorical Variables: Sex, Ethnicity and Geographic Ancestry

The summary will be displayed by “Total” for demographic characteristics.

### **6.4.2. Substance Use**

Substance use, including smoking, alcohol consumption and drug abuse, will be summarized and listed.

The summary will be displayed by “Total”.

### **6.4.3. Medical Conditions**

The CRF texts for medical conditions will be coded using Medical Dictionary for Regulatory Activities (MedDRA), and will be reported using System Organ Class (SOC) and preferred term (PT). A by-subject listing of medical conditions will be provided.

## **6.5. Concomitant Medications**

The CRF texts for concomitant medications will be coded using the WHO Drug Dictionary. A by-subject listing of concomitant medications will be provided.

## 7. SAFETY ANALYSES

The safety analyses will be based on the “Safety” population and displayed separately for each group (Fasting or Fed). Treatment A/B were assigned using safety assessment date or adverse event start date.

The analyses of safety data will be based on GSK Core Data Standards. The details of the planned safety displays are provided in [Appendix 7: List of Data Displays of Full RAP](#).

### 7.1. Extent of Exposure

A by-subject listing of study treatment dosing information will be provided separately.

### 7.2. Adverse Events Analyses

Adverse events analyses include the analysis of adverse events (AEs) and Serious (SAEs).

Adverse events (AEs) will be coded using Medical Dictionary for Regulatory Activities (MedDRA) and grouped by system organ classes (SOCs) and preferred term (PT). AEs will be summarized and grouped by SOC and by PT within SOC. Results will be displayed in the order of decreasing frequency both across SOC and within SOC. In the summary of AEs, the incidence of AEs will be the number of subjects reporting AEs and not the number of AEs reported. Multiple occurrences of the same AE in one individual will be based on each treatment, so subjects will appear in more than one treatment category.

The following summaries and listings will be provided:

- Overview of AEs
- Summary of all AEs
- Summary of all adverse events by maximum intensity
- Summary of all drug-related AEs
- Summary of adverse events leading to withdrawals from study
- Summary of serious adverse events
- Summary of non-serious AEs by system organ class and preferred term
- Listing of all AEs
- Listing of serious adverse events (overall, fatal, non-fatal)
- Listing of all drug-related AEs

- Listing of adverse events leading to withdrawals from study
- Listing of subject numbers for individual adverse events
- Listing of hierarchical relationship of adverse event system organ class, preferred term and verbatim text

The summary will be displayed by treatment group A/B/Total (A: Paroxetine IR 40 mg GSKT tablet; B: Paroxetine IR 40 mg Mississauga tablet).

### **7.3. Clinical Laboratory Analyses**

Laboratory evaluations include the analyses of haematology laboratory tests, chemistry laboratory tests and urinalysis.

The haematology and chemistry data will be summarized and listed separately. Each laboratory test will be summarized at every assessed time point. Parameter values and change from baseline will be summarized separately. The shift tables with respect to normal range will be used to summarize the abnormal laboratory values. By-subject listings of all laboratory data for subjects who had any value of potential clinical importance during the study will be provided. By-subject listings of laboratory values of potential clinical importance only will also be provided.

The urinalysis analysis data will be summarized at every assessed time point.

A listing of laboratory test normal ranges will be provided. A by-subject listing of all laboratory values (including haematology, chemistry and urinalysis analysis) outside the normal reference range will be provided.

The summary will be displayed overall for Screening and by treatment group A/B for post-baseline timepoint (A: Paroxetine IR 40 mg GSKT tablet; B: Paroxetine IR 40 mg Mississauga tablet).

